4.2 Primary Objective

To determine whether intrapartum nipple stimulation changes the likelihood of achieving a spontaneous vaginal delivery compared to receipt of exogenous oxytocin infusion to induce labor.

4.3 Secondary Objectives (if applicable)

The secondary objectives are as follows:

1. To determine if women who perform intrapartum nipple stimulation to induce labor have differences in other obstetric and maternal outcomes such as operative vaginal delivery, cesarean delivery, labor duration, postpartum hemorrhage, infection, and morbidities such as higher-order perineal lacerations, ICU admission, or death.
2. To determine if women who perform intrapartum nipple stimulation report differences in pain scores during labor, labor agency and satisfaction scores, postpartum depression scores, and breastfeeding success scores compared to women who receive only intrapartum exogenous oxytocin infusion.
3. To determine if women who perform intrapartum nipple stimulation report differences in their intention to breastfeed postpartum and their breastfeeding success scores, as well as continuation of breastfeeding for 6 months postpartum. In addition, to determine if neonates of women who perform intrapartum nipple stimulation have differences in breastfeeding as the sole source of nutrition (BSSN) at the time of their birth hospitalization discharge within the first 72 hours and their maximal percent weight loss up to 14 days post-birth compared to neonates of women who receive only intrapartum exogenous oxytocin infusion.
3. To determine if women who perform intrapartum nipple stimulation therapy to induce labor have similar fetal and neonatal outcomes compared to women who receive only intrapartum synthetic oxytocin infusion without nipple stimulation (comparator).
4. To examine the cost-effectiveness of inpatient nipple stimulation therapy via electric breast pump, in comparison to synthetic oxytocin infusion without nipple stimulation (comparator).
5. In a sub-cohort of women who are enrolled in the trial at Yale, to measure circulating plasma concentrations of proteins and microRNA and urinary prostaglandin metabolites using unbiased “omics” approaches, comparing patients undergoing induction of labor via intrapartum nipple stimulation versus continuous exogenous oxytocin infusion.
6. To compare the molecular changes observed with nipple stimulation therapy or continuous exogenous oxytocin infusion with changes seen in early spontaneous labor.
7. In a sub-cohort of women who provide milk samples, we will compare milk composition before and after delivery for the nipple stimulation therapy group to see how the milk is changing and we will compare milk biomarkers after birth between patients undergoing induction of labor via intrapartum nipple stimulation versus continuous exogenous oxytocin infusion.

5 - Study Design

5.1 General Design Description

The proposed study is a multicenter, pragmatic, open label, parallel group randomized trial of nulliparas to compare the effectiveness of intrapartum nipple stimulation therapy with or without adjunctive synthetic oxytocin (intervention) versus immediate synthetic oxytocin

infusion without nipple stimulation (comparator) during labor induction. Potential subjects will be recruited from the Labor & Birth units at three study sites: Yale New Haven Hospital in New Haven, Connecticut, Weill Cornell Medicine in New York, New York and Northwestern Memorial Hospital in Chicago, Illinois. We aim to test the central hypothesis that intrapartum nipple stimulation increases spontaneous vaginal delivery, shortens labor duration, improves other patient-centered outcomes, improves breastfeeding success, and does not increase adverse neonatal and maternal outcomes. We chose a randomized controlled trial, the 'gold standard' of clinical research design, with the goal of obtaining the highest quality evidence to inform clinical practice. Randomly allocating subjects to different interventions minimizes selection bias and results in groups that are comparable with regards to important confounding variables, both measured and unmeasured. Blinding of subjects, maternity care providers, and investigators is not feasible given the intervention being studied (nipple stimulation). With the limitations of the existing data, we estimated our sample size and plan our data analysis based on two-tailed tests. This will ensure that we identify the optimal management strategy for labor induction that increases spontaneous vaginal delivery, irrespective of the direction of our findings.

We will follow the Consolidated Standards of Reporting Trials (CONSORT) guidelines wherever appropriate in the conduct and reporting of this trial. (27) We will use computer-generated random sequences to assign participants to the two interventions with stratification by study site and membrane status (intact versus ruptured). Labor management will be similar in the two groups except for use of nipple stimulation (intervention group) versus immediate synthetic oxytocin infusion without nipple stimulation (control). Analysis will follow the intention-to-treat principle.

5.1.1 Study Date Range and Duration

The study is expected to start in October 2021 at Yale, July 2023 at Northwestern and Spring 2024 at Weill Cornell Medicine and will be conducted over 7 years, with the final participant expected to be enrolled in June 2026. Final data collection and analysis is expected to be completed by June 2028.

5.1.2 Number of Study Sites

The trial will be conducted at three sites: Yale New Haven Hospital (York Street Campus), Weill Cornell Medicine and Northwestern Memorial Hospital.

5.2 Outcome Variables

5.2.1 Primary Outcome Variables

For the main trial, the primary outcome is spontaneous vaginal delivery, defined as a delivery that occurs without the use of forceps, vacuum, or cesarean. This is because spontaneous vaginal delivery is the most desirable outcome for laboring women

5.2.2 Secondary and Exploratory Outcome Variables (if applicable)

The following secondary maternal outcomes will be explored:

- Operative vaginal delivery (defined as delivery with the assistance of forceps or vacuum) and indication
- Cesarean delivery and indication
- Interval from randomization to delivery
- Postpartum hemorrhage (defined as a cumulative blood loss of $\geq 1,000$ mL within 24 hours after the birth process)
- Severe postpartum hemorrhage (defined as any of the following: transfusion; non-elective hysterectomy; use of ≥ 2 uterotonic medications other than oxytocin; other interventions such as uterine compression sutures, uterine artery ligation or embolization, hypogastric artery ligation, balloon tamponade)
- Suspected intraamniotic infection, intrapartum chorioamnionitis, or postpartum endometritis (defined as maternal fever $\geq 38^{\circ}$ Fahrenheit with planned or initiated administration of therapeutic antibiotics) after randomization and prior to delivery hospitalization discharge
- Third- or fourth- degree perineal lacerations
- Lactational mastitis (assessed up to 12 weeks postpartum from breastfeeding survey performed at 4-12 weeks postpartum and medical records)
- Maternal death (assessed until delivery hospitalization discharge)
- Admission to Intensive Care Unit (assessed until delivery hospitalization discharge)
- Subject-reported pain experienced during childbirth using the visual analog scale (28) , measured at 2 hours after start of intervention
- Subject-reported feelings of control during labor using the Labor Agency Scale (29) , assessed during the hospital postpartum stay
- Subject-reported satisfaction with the birthing experience using the validated Birth Satisfaction Scale-Revised (BSS-R) (30) (31), assessed during the hospital postpartum stay
- Subject-reported ability to express and/or collect colostrum and/or breastmilk intrapartum
- Subject-reported perception of milk supply using the validated Perception of Insufficient Milk Supply (PIMS) (40), 2 weeks postpartum

- Subject-reported depression score using the validated Edinburgh Postnatal Depression Scale, assessed (32), 4-12 weeks postpartum
- Subject-reported breastfeeding success using the validated Maternal Breastfeeding Evaluation Scale (MBES) (33), assessed 4-12 weeks postpartum
- Subject-reported breastfeeding success by assessing infant feeding method (breastmilk, formula, or combination) via questionnaire, assessed 6 months postpartum

Among the women enrolled in the translational sub-study at Yale, the following secondary outcomes will be explored:

- Plasma proteomic profiles (measured by mass spectrometry) after 2 hours of treatment comparing patients receiving IV oxytocin and nipple stimulation. Plasma samples from patients who have not undergone cervical ripening will be collected as additional control to account for differences achieved from cervical ripening alone. Plasma samples from patients in early spontaneous labor will be obtained to compare how closely nipple stimulation therapy and IV oxytocin approximate the molecular phenotype of spontaneous labor.
- Changes in plasma proteomic profiles from baseline (prior to treatment), 2 hours, and the time of adequate contractions in each treatment group
- Plasma micro-RNA profiles (measured by bulk RNA sequencing) after 2 hours of treatment among patients receiving IV oxytocin, nipple stimulation, and patients in early spontaneous labor.
- Changes in plasma micro-RNA profiles from baseline (prior to treatment), 2 hours, and the time of adequate contractions in each treatment group
- Urine prostaglandin profiles (measured by mass spectrometry) at 2 hours comparing patients receiving IV oxytocin, nipple stimulation, nipple stimulation who cross-over to IV oxytocin, un-ripened control patients, and patients in spontaneous labor.
- Changes in urine prostaglandin profiles from baseline (prior to treatment), 2 hours, and the time of adequate contractions in each treatment group

Among the women enrolled in the translational sub-study for milk collection, the following secondary outcomes will be explored:

- Changes in milk sodium and conductivity levels from before delivery (in the nipple stimulation therapy group only), and 12, 24, 48 hours after delivery. For mothers hospitalized for a longer period, additional samples at 72 hours will be collected or later up to twice a day.
- Milk macronutrient composition at 48 hours after delivery in each treatment group.
- Milk RNA profile at 48 hours after delivery in each treatment group.

The following secondary neonatal outcomes will be explored:

- Intrapartum fetal death or neonatal death (assessed until birth hospitalization discharge or death)
- Neonatal Apgar score ≤ 3 at 5 minutes of life
- Umbilical cord arterial pH < 7.0 or base excess > 12 mmol/L; or umbilical cord venous pH < 7.0 or base excess > 12 mmol/L if arterial blood sample not available
- Any admission to Neonatal Intensive Care Unit (assessed until birth hospitalization discharge or death)
- Admission to the Neonatal Intensive Care Unit > 24 hours (assessed until birth hospitalization discharge or death)
- Composite neonatal severe morbidity measure including any of the following: Intrapartum fetal death or neonatal death; intubation, continuous positive airway pressure (CPAP) or high-flow nasal cannula (HFNC) for ventilation or cardiorespiratory support within first 72 hours of life; neonatal encephalopathy as defined by Shankaran et al (34) ; seizures; need for hypothermic treatment (cooling); sepsis (defined as presence of a critically ill infant in whom systemic infection is suspected with a positive blood, cerebrospinal fluid, or catheterized/suprapubic urine culture, or in the absence of positive culture(s), clinical evidence of cardiovascular collapse or an unequivocal X-ray confirming infection); pneumonia confirmed by X-ray or positive blood culture; major birth injury (brachial plexus injury, bone fractures, other neurologic injury, retinal hemorrhage, facial nerve injury); meconium aspiration syndrome; intracranial hemorrhage or subgaleal hemorrhage; and hypotension requiring pressor support
- Breastfeeding as the sole source of nutrition (BSSN) at the time of birth hospitalization postpartum discharge within the first 72 hours. This timepoint is chosen because it is the most likely to be causally linked to the study intervention, avoids the risk of attrition bias, and predicts the likelihood of sustained breastfeeding for the recommended 6 months postpartum. BSSN is defined as the infant receiving breastmilk without any supplementary formula or water within the first 72 hours of life. infant feeding method (breastmilk only, mixed feeding which includes both breastmilk and infant formula, or infant formula only) is standardly documented in the EMR at least daily until day of birth hospitalization discharge.
- Maximal percent newborn weight loss up to 14 days post-birth. Maximal percent newborn weight loss is defined as the difference between birth weight and the lowest weight recorded subsequently up to 14 days post-birth, calculated as a percentage of the birth weight, as is typically done daily in clinical practice. Participants will sign a medical release form allowing the study team to obtain/access newborn data in this timeframe, not only from the site's electronic medical record but also from outside

practices/institutions. For the assessment of maximal newborn weight loss, it is standard hospital practice at study sites to regularly weigh each newborn during their birth hospitalization. Infants are weighed naked using a digital scale, and the weight is expressed in kilograms. At the study site, newborns are weighed at birth and then at least daily until day of discharge. The first weight measured after birth is usually performed after at least 6 hours post-birth. Weighing is typically discontinued if the newborn regains his or her birth weight prior to discharge. Infant birth weights are recorded in a standardized fashion in specific EMR flowsheets at study sites. The date and time of each weight are recorded which allows calculation of precise age.

- The following cost outcomes will be assessed: 1) cost of relevant care, and 2) health-related quality of life. Both outcomes will be measured for the mother-infant pair.
 - **Cost of care** will include direct medical cost, direct non-medical care, and indirect cost. Direct medical cost will encompass hospital facility costs and provider professional fees associated with relevant care (maternal labor and delivery hospitalization, newborn's initial birth hospitalization, and infant's postnatal pediatric visits). Direct non-medical cost will account for breast pump use at home, infant formula use, and transportation to relevant care. Indirect cost (i.e., maternal productivity loss) will measure participants' work loss in the postpartum period. As the project will span multiple years, we will use consumer price index to inflation adjust all cost estimates to a constant year U.S. dollars
 - **Health-related quality of life** for participants will be measured by the EuroQol five dimensions (EQ-5D) instrument (41). EQ-5D is a validated instrument for measuring and valuing health. Participants' response to the five dimensions of the EQ-5D descriptive system will be converted to a utility score using a validated U.S. population-based algorithm. Utility score takes values ranging from 0 to 1, with 0 referring to a health state equivalent to death and 1 equivalent to perfect health. EQ-5D is a recommended and widely used instrument for measuring utility score in clinical trials and in maternal health research. For infants, the South Africa EQ-TIPS[™] Paper Proxy 1 questionnaire (previously known as Toddler and Infant (TANDI) Health Related Quality of Life instrument) (42) will be completed by participants (as proxy reporters for their infants). This questionnaire has been shown to be valid and reliable for use in very young children (42). It contains a six-dimension descriptive system (movement, play, pain, social interaction, communication, and eating) with three severity levels (no, some, or a lot of problems), along with a visual analogue scale (VAS) assessing an infant's overall health. As utility score based on the EQ-TIPS[™] descriptive system has not been developed yet, we will linearly transform the VAS score to a utility score on a 0 to 1 scale.

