6.2 Assessments

Obstetric and perinatal clinical outcomes will be assessed and abstracted through chart review of the electronic medical record of both subjects and their infants by certified trained research members according to the outcome definitions listed in the protocol. Postpartum assessments will be conducted at 2 weeks postpartum and 4-12 weeks postpartum. While the ideal time period is 6-8 weeks postpartum, such a short time-window for follow-up may result in less-than-ideal protocol adherence, and 12 weeks is still within the typically described postpartum period (the “4th trimester”). In addition, economic costs and infant feeding method will be assessed at 6 months postpartum.

To assess patient-centered outcomes, several study questionnaires will be conducted:

1. To assess subject-reported pain experienced during childbirth, the visual analog pain scale (28) will be administered at three different timepoints: (1) prior to initiating study intervention (to obtain baseline); (2) two hours after initiating study intervention; and (3) during postpartum stay prior to delivery hospitalization discharge.
2. To assess subject-reported satisfaction with the childbirth process, the Birth Satisfaction Scale-Revised (BSS-R) (30) (31) will be administered during postpartum stay prior to delivery hospitalization discharge.
3. To assess subject-reported feelings of control during childbirth, the Labor Agency questionnaire (29) will be administered during postpartum stay prior to delivery hospitalization discharge.

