4. To assess subject-reported feelings of depression after childbirth, the Edinburgh Postnatal Depression Scale (EPDS) (32) will be administered at two different timepoints: (1) prior to initiating study intervention (to obtain baseline) and (2) at 4-12 weeks postpartum (ideally 6-8 weeks postpartum). The baseline EPDS will be reviewed, and the total score will be tabulated in real-time. The EPDS at 4-12 weeks postpartum will be completed by the subject online or with a certified study team member via telephone. A certified study team member will check daily (Monday-Friday) to review any completed online surveys and tabulate scores during these daily (Monday-Friday) reviews. If the EPDS at 4-12 weeks postpartum is completed with the subject via telephone, the total score will be tabulated at the conclusion of the telephone encounter. Any score ≥ 10 on either the baseline or 4-12 weeks postpartum EPDS will be reported to the subject's primary obstetric provider team as this is the threshold that suggests increased risk of depressive illness.
5. Prior to delivery hospitalization discharge, subjects will be asked if they had any intrapartum expression of colostrum or breast milk, the quantity (mL or ounces) expressed if known, whether they collected and stored it for their infant, and whether they fed it to their infant.
6. After delivery hospitalization discharge 2 weeks postpartum, all subjects will be administered the Perception of Inadequate Milk Supply (PIMS) (40) survey to assess their perception of their milk supply. In addition, the EQ-5D[™] and EQ-TIPS[™] surveys will be administered.
7. After delivery hospitalization discharge, between 4 to 12 weeks postpartum (ideally 6 to 8 weeks postpartum), all subjects will be contacted by text message, telephone, or by email (based on subject preference) to evaluate if they experienced any unanticipated outpatient or inpatient visits for them or their infants since delivery hospitalization discharge. Subjects will also be asked if they ever attempted to breastfeed postnatally.
8. Among subjects who state they attempted to breastfeed at least once postnatally; these subjects will be administered the Maternal Breastfeeding Evaluation Scale (MBES) (33) between 4 to 12 weeks postpartum (ideally 6 to 8 weeks postpartum) to assess their breastfeeding success. In addition, the EQ-5D[™] and EQ-TIPS[™] surveys will be administered.

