Subjects will be administered study questionnaires at multiple timepoints, as outlined below. Questionnaires will be administered using the REDCap Survey tool, and electronic QR codes will be provided to the subjects via email or text message (whichever the subject prefers). Paper versions will also be available if requested.

After randomization, subjects will be asked to complete four questionnaires to establish baseline: the visual analog pain scale (28), the Edinburgh Postnatal Depression Scale (EPDS) (32), the Infant Feeding Intention Scale (IFI) (39), and the EQ-5D survey (41). Two hours after initiation of study intervention, subjects will again be asked to complete the visual analog pain scale (28) to assess their pain after intervention start.

During their hospital postpartum stay prior to discharge, subjects will be asked to complete three questionnaires: the visual analog pain scale (28) to rate their pain experienced during childbirth; the Labour Agency scale (29) to assess their feelings of control during childbirth; and the Birth Satisfaction Scale-Revised (BSS-R) (30) (31) to rate their satisfaction with the childbirth process. They will also be asked about whether they plan to attempt to breastfeed their infant. They will also be asked if they had any intrapartum expression of colostrum or breast milk, the quantity (mL or ounces) expressed if known, whether they collected and stored it for their baby, and whether they fed it to their baby.

After hospital discharge (preferably two weeks postpartum, but up to three weeks postpartum will be acceptable), all subjects, regardless of study group, will be asked to complete one questionnaire: the Perception of Milk Supply (40). The unique QR code or link to this electronic survey will be emailed or texted to the subject based on their preference. Follow-up phone call will be made if needed.

After hospital discharge (preferably six to eight weeks postpartum, but anytime within the window of four to twelve weeks postpartum will be acceptable), all subjects, regardless of study group, will be contacted to ask about any unanticipated outpatient or inpatient visits for them or their infants since discharge. Subjects will also be asked to complete two questionnaires: the Maternal Breastfeeding Evaluation Scale (33) and the EPDS (32).

After hospital discharge (6 months postpartum), all subjects will be asked to complete one questionnaire to assess infant feeding method.

Biospecimen Procedures:

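### Lactational mastitis is defined to 12 weeks postpartum, but self-report ends on a survey day between weeks 4 and 12, leaving later onsets to medical records of unclear reach

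*Protocol*

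**What the plan says.** Protocol section 5.2.2 gives the mastitis outcome its horizon and its two sources in one phrase: "assessed up to 12 weeks postpartum from breastfeeding survey performed at 4-12 weeks postpartum and medical records".

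Section 6.3 (Subject Management and Follow-Up) sets the timing of that contact: "preferably six to eight weeks postpartum, but anytime within the window of four to twelve weeks postpartum will be acceptable". Section 6.2 says the same ("While the ideal time period is 6-8 weeks postpartum") and explains that the wider window is meant to protect adherence. At this contact women are also asked about unplanned care, to "evaluate if they experienced any unanticipated outpatient or inpatient visits for them or their infants since delivery hospitalization discharge". That question looks back from the day of contact. Section 6.2 gives the breastfeeding scale only to some women: "Among subjects who state they attempted to breastfeed at least once postnatally".

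The only later contact is at 6 months, when "all subjects will be asked to complete one questionnaire to assess infant feeding method". Sections 6.2 and 6.3.1 add two quality-of-life instruments. No mastitis question is described there.

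Three passages bear on records. Section 6.2 says clinical outcomes are "abstracted through chart review of the electronic medical record of both subjects and their infants". Section 7.5 describes review of the record of each woman's hospital stay. Section 5.2.2 describes a release covering outside institutions, but for infants and within the 14-day weight-loss window: "Participants will sign a medical release form allowing the study team to obtain/access newborn data in this timeframe".

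Section 6.4.3.1 compares categorical secondary outcomes as proportions, with a chi-squared or Fisher test and a relative risk.

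**The concern.** The definition gives every woman the same 12-week horizon, but self-report covers only the time up to the day she answers. Take two women who each develop mastitis at week 7 and are treated somewhere the study chart does not reach. The one surveyed at week 11 is counted and the one surveyed at week 4 is not. A simple comparison of proportions treats both as observed to week 12.

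This is a breast-related harm in a trial of breast stimulation, and section 6.4.3.3 relies on comparing maternal morbidity outcomes to pick up safety signals. At stake are the absolute mastitis rate that would be reported and, under some conditions, the comparison between arms.

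**Working it through.** The protocol gives no mastitis rate, onset pattern or capture rate for records, so there is no figure to reproduce. What can be worked out is the length of the gap and the range of its effect.

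**Inputs from the protocol.** Horizon: 12 weeks (5.2.2). Survey week *t*: 4 to 12, preferably 6 to 8 (6.2, 6.3).

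**Assumptions, none from the protocol.** Onset is uniform over 0-12 weeks, or its rate declines at *d* = 0.1 or 0.3 per week. Records capture a share *s* of onsets after the survey, with *s* = 0, 0.5, 0.8 or 1. The survey captures every onset before it.

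**Step 1: weeks without self-report = 12 - *t*.**
- Week 4: 8 weeks (67% of the window)
- Week 6: 6 weeks (50%)
- Week 8: 4 weeks (33%)
- Week 12: 0 weeks

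Coverage thus differs between women by up to 12 - 4 = 8 weeks. At the preferred timing, 4 to 6 weeks have no self-report.

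**Step 2: share of 12-week onsets falling after the survey.** Uniform: *L* = (12 - *t*)/12. Declining: *L* = (e^(-*dt*) - e^(-12*d*)) / (1 - e^(-12*d*)). For example, with *d* = 0.3 and *t* = 6: (0.1653 - 0.0273)/(1 - 0.0273) = 0.142.

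**Step 3: share missed = *L* × (1 - *s*).** Each cell shows *s* = 0 / 0.5 / 0.8 / 1.

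| Survey week | Uniform onset | Decline 0.1 per week | Decline 0.3 per week |
|---|---|---|---|
| 4 | 67 / 33 / 13 / 0% | 53 / 26 / 11 / 0% | 28 / 14 / 6 / 0% |
| 6 | 50 / 25 / 10 / 0% | 35 / 18 / 7 / 0% | 14 / 7 / 3 / 0% |
| 8 | 33 / 17 / 7 / 0% | 21 / 11 / 4 / 0% | 6.5 / 3.3 / 1.3 / 0% |

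The loss runs from nothing to two thirds. It depends on the onset pattern and above all on *s*, the quantity the protocol leaves unclear.

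**Step 4: effect on the relative risk.** Let *c* = 1 - *L*(1 - *s*) be the share captured in an arm. The observed relative risk is the true one multiplied by *c*(stimulation)/*c*(oxytocin).
- Same survey timing, onset pattern and record capture in both arms: the ratio is 1 and the relative risk is unbiased. Only the absolute rate and the precision suffer.
- Illustration of different timing: one arm surveyed at week 6 and the other at week 8, uniform onset, no record capture. The ratio is 0.500/0.667 = 0.75. With *s* = 0.5 it is 0.750/0.833 = 0.90.
- Illustration of different time at risk: both arms surveyed at week 6 with no record capture, but onset uniform in the stimulation arm and declining at 0.1 per week in the oxytocin arm. The ratio is 0.500/(1 - 0.354) = 0.77. Section 4.1 hypothesises more sustained breastfeeding with stimulation, which would push in this direction.

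These are illustrations; nothing in the protocol shows that either difference will occur.

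**The case against.** A reader might infer that time after the survey has no ascertainment at all. The documents do not support that. Section 5.2.2 names medical records as a second source with no cut-off at the survey day, and section 6.2 has charts reviewed for the women as well as their infants. The supportable statement is that post-survey time rests on records alone. What remains unsettled is how far those records reach: section 7.5 speaks only of the hospital stay, and the one release described for outside records concerns newborns. The consent form and data collection form are not in the available text and may say more, so this reach is unclear rather than shown to be missing.

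A reader might also infer that a stated 12-week rate is too low. No such rate is stated, and the phrase could be read as an outer bound set by the survey window. On that reading, however, the women still have unequal observation, which the comparison of proportions ignores.

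The same contact schedule applies in both arms, and if late cases are missed in equal proportion the relative risk is unbiased. That stands, subject to the two conditions worked through in step 4. The wide window is also a deliberate, explained choice, and it need not change. Variable follow-up could be handled in an analysis plan that is not shown, but the protocol itself fixes the horizon, the sources and a simple comparison of proportions, and these do not fit together.

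**Conclusion.** The point holds as a mismatch between the outcome horizon and the self-report window. Self-report coverage differs between women by up to 8 weeks, and 4 to 6 weeks lack it even at the preferred survey time. Undercounting of late mastitis is likely, but its size cannot be found from the documents. Under the assumptions above it is 0% if records capture every late event and 67% at the extreme of a week-4 survey, uniform onset and no record capture. If records capture half of the late events, a week-6 survey loses 7% to 25%.

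Bias between arms is possible but not shown. It requires survey timing, response or late time at risk to differ by arm. The open-label design and the hypothesis of longer breastfeeding make this worth checking. This is one secondary outcome among many, so the matter is a worthwhile improvement rather than a threat to the trial's main conclusion.

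**What to change.** In section 5.2.2, take one of two routes.

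1. Record the date of mastitis onset on the existing 4-12 week survey and from records, and replace the simple proportion with time from birth to first mastitis, censored at the last date of ascertainment. Fix that date by a rule that does not depend on whether an event was found. It could be the survey date, or week 12 if records are reviewed that far for everyone. Counting late record-based events while censoring other women at the survey would bias the rate upward.
2. Add a mastitis item with onset date to the existing 6-month survey, so that self-report covers the whole 12-week window.

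With either route, state that maternal records are reviewed to week 12 for every woman, reconcile sections 5.2.2, 6.2 and 7.5 on which records these are, and report survey timing and response by arm.

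The cost is one dated item on an existing questionnaire and a few sentences of protocol. The 6-month item brings longer recall. Enrolment began in October 2021, so women already past the relevant survey would have onset dates only from records, and results should be shown separately for women surveyed before and after the change. Restricting the outcome to onset within 4 weeks would equalise the window among responders, but it gives up later events and still needs onset dates from women surveyed later.
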